9.2 Serious Adverse Events

9.2.1 Definition of serious adverse events

- 1. serious adverse event can be defined as any of the following.
- 1) Deadly or life-threatening.
- 2) requiring hospitalization or extended hospitalization.
- 3) Resulting in significant or lasting disability or functional impairment.
- 4) causing a congenital anomaly or birth defect
- 5) medically significant and serious illness that endangers the patient's health and requires medical intervention or surgical intervention to prevent any of the above outcomes.
 - 2. The following admissions are often not considered serious adverse events.
- 1) Discharge or withdrawal of the patient for progressive exacerbation of the disease requiring hospitalization or extended hospitalization.
- 2) Hospitalization for routine treatment or observation for indications involved in the trial that are not accompanied by a worsening of the disease;

3) the patient's hospitalization was planned prior to enrollment in this trial and no exacerbation of symptoms that existed prior to the trial was observed

4) Treatment is received only in an emergency, outpatient setting that does not meet any

of the above definitions of a serious adverse event and does not require hospitalization.

5) The pregnancy itself is not a serious adverse event, but should be reported on a serious

adverse event form or pregnancy record form and should be followed up as well as the

outcome documented, including spontaneous abortion or voluntary termination of pregnancy,

details of the birth of the infant, and the presence of congenital anomalies and birth defects.

9.2.2 Reporting of serious adverse events

If a Grade 5 serious adverse event occurs in a healthy volunteer during the course of the

study (from the date of signing the informed consent to the last visit) and may be related to

the study drug treatment, the investigator must complete a serious adverse event report form

and report it to the ethics committee of the study center where the event occurred within 24

hours of learning of the event, and the investigator must sign and date the report.

Medical Ethics Committee of the Hospital of Hematology, Chinese Academy of Medical

Sciences (Institute of Hematology, Chinese Academy of Medical Sciences)

Contact: [name] [contact]; E-mail: [contact]

Address: [name]

Data Management

This study used the Case report form (CRF) for data collection. A dedicated person was

developed to enter the contents of the CRF into the database, and a dedicated person verified

the consistency of the database with the CRF data. The data manager checked the data in the

database according to the clinical study protocol, and if there were any questions, a

questionnaire was filled out and the questions in the questionnaire were answered by the

investigator.

11 **Statistical Methods**

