9.1.2 Adverse event collection and recording

Adverse events from the date of signed informed consent to the last visit were recorded, and the investigator applied concise medical terminology to report all possible treatment-related adverse events.

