9.1.3 Criteria for determining the severity of adverse events

Use the National Cancer Institute Common Terminology Criteria for Adverse Events (CTCAE) version 5.0 to document the severity of adverse events on a scale of 1-5

Grading	Criteria
1	Mild; asymptomatic or mild; seen clinically or diagnostically only; no
1	treatment required
2	Moderate; requires lesser, localized or non-invasive treatment; age-
2	appropriate limitation of instrumental activities of daily living*
	Severe or medically significant but not immediately life-threatening;
3	resulting in hospitalization or prolonged hospitalization; disabling; limiting
	personal activities of daily living \triangle
4	Life-threatening; requires urgent treatment
5	AE-related deaths

^{*} Instrumental activities of daily living: refers to cooking, buying clothes, using the telephone, managing money, etc.

 \triangle Personal activities of daily living: refers to bathing, dressing and undressing, eating, toileting, taking medication, etc., and not bedridden.

Note: the distinction between severity and intensity of the adverse event. Severity is used to describe intensity and is not necessarily an SAE. e.g. a headache may be severe in intensity but cannot be included in an SAE unless it meets SAE criteria.

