9.1.4 Criteria for judging the relationship between adverse events and study drug therapy

The investigators analyzed the relevance of adverse events to the study drug treatment according to the principle of determining the relevance of adverse events to the study drug

treatment, which was divided into 5 categories, namely "definitely related, probably related, probably unrelated, definitely unrelated, and undetermined", and "definitely related, probably related, probably unrelated, and The adverse reactions were classified as "definitely related, probably related, probably unrelated and undetermined". The investigator must document the adverse reactions using medical terminology.

	Is it reasonable Time relationship	Is it consistent with known Type of adverse reaction	Whether there are other reasons for The possibility of adverse	
	Time relationship	Type of adverse reaction	events	
Definitely related	Yes	Yes	Yes	
Possibly related	Yes	Yes / No	Uncertain	
Possibly unrelated	No	No	Uncertain	
Definitely not related	No	No	Yes	
Unable to judge	Required information for evaluation is not available			

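### The 24-hour SAE reporting rule is triggered only by deaths, so non-fatal serious adverse events have no stated route to the ethics committee

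*Protocol*

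**What the plan says.** Section 9.2.2 (Reporting of serious adverse events) opens its rule with "If a Grade 5 serious adverse event occurs in a healthy volunteer during the course of the" study, and adds that the event may be related to the study drug. When both conditions are met, the investigator must complete the SAE form "and report it to the ethics committee of the study center where the event occurred within 24" hours of learning of it. The rule covers the time from consent to the last visit.

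Section 9.1.3 grades severity from 1 to 5 by CTCAE 5.0 and gives Grade 5 as "AE-related deaths". A note under that table keeps grade and seriousness apart: "Severity is used to describe intensity and is not necessarily an SAE".

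Section 9.2.1 defines seriousness by five criteria. The first is "Deadly or life-threatening" and the third is "Resulting in significant or lasting disability or functional impairment". The others are hospitalisation, congenital anomaly, and medically significant illness needing intervention.

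Section 9.1.2 says that "the investigator applied concise medical terminology to report all possible treatment-related adverse events", without naming a recipient, a form or a deadline.

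**The concern.** The protocol defines an SAE by outcome, warns that grade is a different scale, and then uses grade to decide which SAEs are reported. The grade it uses is the one reserved for death. A site that follows 9.2.2 to the letter would send the ethics committee a possibly drug-related death, but not a drug-related life-threatening event or hospital admission.

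The participants are healthy volunteers, and safety is part of the primary objective. The weekly calls in section 7.2 would bring a serious event to the investigator while other volunteers are still being dosed. From there, no stated rule takes it to the ethics committee. What is at stake is the timing of outside oversight, not the primary endpoint or its analysis.

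**Working it through.** No figure in the protocol needs to be reproduced. The check sets the trigger in 9.2.2 beside the grade table in 9.1.3 and the definition in 9.2.1, and then looks for any other rule that would cover the remainder.

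**Step 1: which serious outcomes can meet the trigger.** Criterion 1 of 9.2.1 names two outcomes and criteria 2 to 5 name one each: 2 + 4 = 6.

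| Serious outcome (9.2.1) | Place in the grade table (9.1.3) | Meets the Grade 5 trigger? |
|---|---|---|
| Death | 5, if AE-related | Yes, if it may also be drug-related |
| Life-threatening | 4 | No |
| Hospitalisation, new or prolonged | 3 | No |
| Disability or functional impairment | 3 (disabling) | No |
| Congenital anomaly or birth defect | Not named; below 5 unless fatal | No |
| Medically significant illness | 3 (medically significant) | No |

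One outcome meets the trigger, and 6 − 1 = 5 do not. This counts categories in the definition. It does not measure how often each would occur.

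**Step 2: the relatedness condition.** The rule needs both Grade 5 and possible relatedness, so a death judged unrelated is outside it too. Section 9.1.4 has five causality categories, and 9.2.2 does not say which of them count as possibly related. A poorly translated sentence in 9.1.4 appears to treat four of the five, "definitely related, probably related, probably unrelated and undetermined", as adverse reactions. If those four are what 9.2.2 means, it does not say so.

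**Step 3: other text that might close the gap.**
- Section 9 and section 11.3 have AEs recorded, assessed for causality and described. Neither names a recipient or a deadline.
- Section 9.1.2 asks for reporting of possibly related events, again with no recipient, form or deadline.
- Section 9.2.1 sends pregnancies, which it says are not SAEs, to an SAE or pregnancy form with follow-up that includes congenital anomalies. It gives no recipient or deadline.
- Section 12.1 refers in general to regulations and ethics committee review and states no SAE rule.
- Section 12.2 requires the consent form to be revised and re-approved if important new data emerge. That is not an SAE rule and sets no deadline.

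None of these gives a non-fatal SAE a recipient and a deadline.

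**Step 4: the time during which early reporting could protect others.** The abstract plans 3 weeks of enrolment and 4 weeks of dosing per volunteer, so dosing is under way in at least some volunteers for up to 3 + 4 = 7 weeks after the first enrolment. The reporting gap itself lasts longer, because 9.2.2 runs to the last visit.

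**The case against.** The strongest reply is that a narrow expedited threshold does not logically contradict a wide SAE definition. A sponsor may choose to expedite only some SAEs, and no text in the protocol says that all must be. That is right as logic. But the section presents itself as the reporting rule for SAEs, and it selects them by a scale that the protocol itself says is not a measure of seriousness. Nothing else in the text provides for the remainder.

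A second reply is that Grade 5 may be a translation slip, perhaps for the five criteria of 9.2.1. That is quite possible in a document with other rough wording. It bears on what the sponsor intended, but the term is defined in 9.1.3 and staff will act on the text, so the correction is needed either way.

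Third, other safeguards exist: events are recorded, graded and assessed for causality, the investigator can stop an individual's treatment (5.3), pregnancies have a form, and general regulations apply. These stand, and they limit the consequence. They do not supply the missing recipient and deadline. The annexes show no content, so a procedure there could not be checked, although 9.2.2 does not refer to one.

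Finally, the count of five out of six says nothing about risk. That is correct, and the conclusion does not depend on it.

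**Conclusion.** The concern holds. Read with the protocol's own definitions, the only visible SAE rule with a recipient and a deadline covers possibly drug-related deaths and nothing else. Non-fatal SAEs, including those judged definitely related, have no stated route to the ethics committee. Five of the six outcomes named in 9.2.1 are affected. No number of events can be given, because the protocol states no SAE rate.

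This rests on two things: that Grade 5 carries the meaning given in 9.1.3, and that no procedure outside the visible text fills the gap. It should be corrected as a matter of participant protection. It does not bear on the validity of the efficacy result.

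**What to change.** Reconcile 9.2.2 with 9.2.1 by replacing the Grade 5 trigger with a serious adverse event as defined in 9.2.1. The sponsor should also state whether the relatedness condition stays. If it does, 9.2.2 should list which of the five categories in 9.1.4 satisfy it, and the sentence in 9.1.4 that classes categories as adverse reactions should be cleaned up so that the two sections agree.

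This rewords one sentence in 9.2.2 and clarifies another in 9.1.4. Visits, data collection, sample size and analysis do not change. The cost is some additional expedited reports and ethics committee workload, less if the relatedness condition is kept. It cannot be quantified without an SAE rate, but is likely to be small among a planned 130 healthy volunteers.

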11.1 Sample size

The primary endpoint of this study was the rate of novel coronavirus infection in healthy

volunteers. The historical novel coronavirus infection rate was estimated to be about 35%, and

10

the experimental group was expected to control the infection rate at about 20%, taking a two-sided α =0.05 with a test efficacy of 90%, and a sample size of 100 cases was calculated using a one-sample rate difference z-test continuity correction method, taking into account the 20% shedding rate and personnel position stratification factors, and 130 healthy volunteers were expected to be enrolled in the final study. The allocation ratios by personnel position were as follows: physicians: 20; nurses: 30; medical technicians: 20; managers: 20; researchers: 20; and medical students: 20.

11.2 Statistical analysis set

Full analysis dataset (FAS): is a dataset determined according to the Intention-To-Treat (ITT) principle and includes all enrolled healthy volunteers who have used the study drug at least once and have at least one analyzable efficacy indicator, and validity analysis is based on the FAS.

Protocol-compliant dataset (PPS): a subset of the overall FAS, including healthy volunteers who did not show significant protocol deviations in the full analysis set, used as an adjunct to the validity analysis.

Safety data set (SS): all healthy volunteers enrolled who received the trial drug and had at least one post-dose safety evaluation data, safety analysis was based on SS.

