Statistical Methods:

SAS 9.4 software was used for statistical analysis of the data in this study, with continuous variables described by mean \pm stan dard deviation (Mean \pm SD) or median, maximum, minimum, and interquartile range (Median, Max, Min, IQR) and categorical variables described by rate or percentage. Comparisons of measurement data were performed by t-test/ANOVA or nonparametric test; comparisons of count data were performed by $\chi 2$ test or Fisher's exact probability test. If not otherwise specified, all tests were performed as two-sided tests with a test level of α =0.05.

2 Research Background

Researchers at the University of Cambridge, UK, and other institutions have found that ursodeoxycholic acid (UDCA) is able to turn off the ACE2 receptor, thereby blocking viral entry into human cells, and since the SARS-CoV from 2003 to the SARS-CoV-2 spectrum in 2019 utilizes ACE2 as the primary invasion receptor, even if subsequent SARS-CoV-2s continue to show new small variants, the drug maintains its effect. The study was published in Nature on December 5, 2022, entitled "FXR inhibition may protect from SARS-CoV-2 infection by reducing ACE2" [1]. Ursodeoxycholic acid (UDCA) was found to downregulate angiotensin-converting enzyme 2 (ACE2) expression by inhibiting the transcription factor FXR, thereby shutting down the entry of neocoronavirus into human cells. Since the drug acts on the host cell and not on the virus itself, it may be able to prevent current neo-coronavirus infections and should also be able to prevent future neo-coronavirus new mutants, as well as infections by other coronaviruses that utilize ACE2. Currently, China is in a period of high prevalence of neo-coronavirus infections, and there is an urgent need for clinical studies on prophylactic drugs

3 Research objectives

The purpose of this study is to evaluate whether ursodeoxycholic acid is an effective prophylactic agent against novel coronavirus (SARS-CoV-2) infection in medical personnel

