3.2 Secondary research objectives

- 1) To explore the evaluation of the transition to severe disease in the population infected with novel coronavirus;
- 2) To explore the evaluation of the persistence and reduction of symptoms in people infected with novel coronavirus;
- 3) To explore the evaluation of antibodies in a population of healthy volunteers;
- 4) To observe the safety of ursodeoxycholic acid drugs;
- 5) To evaluating the changes of S protein-specific T/B cell immunity before and after BF.7 infection after immunization with Wuhan Strain vaccine.

4 Study design

This is a single-center, open-ended, single-arm clinical study to evaluate the effectiveness of daily ursodeoxycholic acid plus routine protective measures for the prevention of novel coronavirus infection. The target sample size is 130 medical workers and each healthy volunteer will be followed weekly for nucleic acid/antigen testing or disease progression over an 8-week period for new crown infections.

5 Study population

Healthy volunteers for this study were drawn from medical workers who were not infected with novel coronavirus

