7.3 Follow-up period (8 weeks)

1) If a healthy volunteer develops novel coronavirus symptoms during the follow-up period, the volunteer's symptoms will be scored and recorded according to Table 1.

Table 1: New crown symptom assessment form

Symptoms	Rating				
	Slight =1	Medium =2	Serious =3	Score	
Abdominal					
pain					
fatigue					
Cough					
Shortness of					
breath					
Diarrhea					
Muscle pain					
Headaches					
Taste and					
smell disorder					

Other		
Total Score		

- 1) Weekly telephone follow-up of AE status of healthy volunteers.
- 2) Detection of antibodies before and after drug administration.
- 3) Weekly monitoring of nucleic acid/antigen status of new crowns in healthy volunteers during the study period, and testing for nucleic acid at any time during the study period when volunteers develop symptoms of novel coronavirus (in case of positive self-test antigen, this can be substituted for nucleic acid results)./
- 4) Blood will be collected for freezing and storage in case of infection and out of the group.

Table 2: Table of observation items during the visit

	Baseline period	Detection frequency	In case of infection
Demographic Information	√		
Nucleic acid testing	√	Weekly	√
Vital signs	√		
AE Telephone follow-up AE	√	Weekly	
Blood collection for freezing and storage	√	Week 4 and 8	

[figure not shown]

Figure 1: Research flow chart

[figure not shown]

Figure 2: Flow chart of the visit

8 Research indicators

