8.1 Primary research indicators

Prevalence of novel coronavirus infection in healthy volunteers receiving 4 weeks of continuous ursodeoxycholic acid plus conventional protection during the study period, the proportion of healthy volunteers infected with novel coronavirus during the study period as a percentage of the study population

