11.3 Statistical analysis methods

SAS9.4 software was used for statistical analysis of the data in this study, and all tests were performed by two-sided test with test level α =0.05 if not otherwise specified.

(1) Basic methods

The measurement data were described by mean \pm standard deviation (Mean \pm SD) or median, maximum, minimum, and interquartile range (Median, Max, Min, IQR); the count data were counted as number of cases and described by rate or percentage; the comparison of measurement data was performed by t test or nonparametric test; the comparison of count data was performed by χ^2 test or Fisher's exact probability test.

2 Analysis of primary endpoint indicators

The number and percentage of healthy volunteers with new coronavirus infection were calculated, and 95% exact confidence intervals were calculated using the Clopper-pearson method.

③ Analysis of secondary endpoint indicators

The $\chi 2$ test or Fisher's exact probability test was used to compare the proportion of neo-coronavirus-infected patients in different subgroups who turned to severe disease and the proportion of neo-coronavirus-infected patients without symptoms, and to calculate the confidence interval respectively; the number of days describing the duration of symptoms such as fever and sore throat in infected patients and the number of days to turn negative were calculated; the antibody status of all healthy volunteers and neo-coronavirus-infected patients were described separately.

4 Analysis of safety indicators

The occurrence of adverse events AE and serious adverse events SAE were recorded and described, and the relevance of the events to the study was determined.

(5) Other analyses

Subgroup and stratified analyses were performed on people of different genders, age groups, staff positions, and staff sections to explore the relationship between the levels of different factors and the effects of neo-coronavirus infection.

12 Ethics Review

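### The crude infection percentage in the one-dose, one-result FAS can count early leavers as uninfected, and 8.1 and 5.4 do not line up with that analysis set

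*Protocol*

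**What the plan says.** Section 11.2 follows the intention-to-treat principle and names the FAS as the set for efficacy. The FAS "includes all enrolled healthy volunteers who have used the study drug at least once and have at least one analyzable efficacy indicator". It sets no minimum follow-up. The per-protocol set (PPS) removes significant deviations and is only an adjunct.

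Section 11.3 fixes the primary analysis: "The number and percentage of healthy volunteers with new coronavirus infection were calculated", with an exact 95% Clopper-Pearson interval. It mentions no allowance for incomplete follow-up.

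Section 8.1 defines the endpoint in two clauses. The first is "Prevalence of novel coronavirus infection in healthy volunteers receiving 4 weeks of continuous ursodeoxycholic acid plus conventional protection during the study period". The second is "the proportion of healthy volunteers infected with novel coronavirus during the study period as a percentage of the study population". Neither names an analysis set.

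Section 11.1 assumes a historical rate of 35% and an expected rate of 20%, calculates 100 volunteers, and enrols 130, "taking into account the 20% shedding rate" and the staff-position quotas.

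Section 5.3 takes volunteers off study for, among other reasons, missed visits. Section 5.4 removes poor compliers and users of other prophylactics from the study. Section 7.3 plans "Weekly monitoring of nucleic acid/antigen status of new crowns in healthy volunteers during the study period", and section 4 says that "each healthy volunteer will be followed weekly for nucleic acid/antigen testing or disease progression over an 8-week period".

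**The concern.** Infection accrues over time. A volunteer who takes one dose, has one negative test and then leaves meets the FAS definition if that test is an analyzable indicator. If testing stops at that point, a later infection is never seen, yet the volunteer stays in the denominator. The crude percentage treats unknown as uninfected.

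In a randomised comparison both arms would share such loss to some degree. Here there is one arm, and the only benchmark is the external 35% in 11.1. The protocol itself allows for 20% loss, so the situation is foreseen. At stake is a primary rate that looks better than the drug deserves.

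Two wording problems add to this. Section 8.1 leaves open whether the four-week phrase describes the regimen or limits the denominator to completers. Section 5.4 does not say whether results already collected from removed volunteers stay in the FAS.

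**Working it through.** **1. The plan's own figure.** Inputs from 11.1: 35%, 20%, two-sided 0.05, power 90%, continuity-corrected one-sample z-test.

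- n = [(1.960 × √(0.35 × 0.65) + 1.2816 × √(0.20 × 0.80)) / 0.15]² = 93.1
- Corrected: n/4 × (1 + √(1 + 2/(n × 0.15)))² = 99.7, so 100.
- Shedding alone: 100 / 0.8 = 125. The quotas 20 + 30 + 20 + 20 + 20 + 20 give 130.

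The sample size reproduces and is not in question.

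**2. Direction.** Let d be the share who leave early, p the full-follow-up risk, and m a leaver's mean risk up to the last test. The expected crude FAS rate is (1 − d) × p + d × m. Since m cannot exceed p, this is at or below p.

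**3. Size (illustration).** Assumptions: p = 35%; n = 130; weekly tests over 8 weeks; non-informative loss spread evenly after tests 1 to 7; success read as an exact upper limit below 35%. Section 11.3 states no such rule. The rule allows at most 34 infections of 130 (upper limit 34.6%; 35 infections give 35.4%). With no loss, P(X ≤ 34 | 130, 0.35) = 2.0%.

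The protocol does not give the time course of infection. Section 2 says "Currently, China is in a period of high prevalence of neo-coronavirus infections", so infections may fall early. Three shapes, each scaled to reach 35% at week 8:

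| Weekly hazard | m | Crude rate, d = 10% | False success | Crude rate, d = 20% | False success |
|---|---|---|---|---|---|
| Constant | 18.9% | 33.4% | 4.7% | 31.8% | 9.8% |
| Halves every 2 weeks | 26.7% | 34.2% | 3.1% | 33.3% | 4.8% |
| Halves every week | 30.8% | 34.6% | 2.5% | 34.2% | 3.1% |

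Example: 0.8 × 0.35 + 0.2 × 0.189 = 0.318. At 20% loss the shortfall is 0.8 to 3.2 points.

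**4. Bounds without a time course.** Let f be the fraction of a leaver's risk that is observed (m = f × p), with 26 leavers and 104 completers. The expected crude rate is 28.0% at f = 0, 31.5% at f = 0.5 and 35.0% at f = 1. False success is 35.1%, 10.8% and 2.0%. The three shapes above correspond to f of about 0.54, 0.76 and 0.88 (m / 0.35).

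**5. Alternative estimator.** Kaplan-Meier on the same weekly data, simulated (20,000 runs) over the three shapes at 10% and 20% loss, averages 35.0% with false success of 1.9% to 2.1%.

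**The case against.** Several objections have force.

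*The analysis set is named.* A reader might infer that 8.1, 11.1 and 11.2 set three competing denominators. The text does not support that. Section 11.2 names the FAS for efficacy. The four-week phrase in 8.1 can describe the regimen, and its second clause fits the FAS. Section 11.1 defines no denominator: inflating for dropout is ordinary planning, and 130 reflects position quotas as well as shedding. What stands is that 8.1 should say FAS.

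*The direction is conditional.* A reader might infer that the crude rate can only understate infection relative to the historical 35%. That goes too far. The 35% has no stated window or method and could itself be incompletely observed. Section 11.2 does not say that one negative test is analyzable, and no section says that testing ends when a volunteer leaves. The bias is zero if leavers have no later infection or are still tested.

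*The size depends on assumptions.* The 20% is a planning allowance, the success rule is assumed, and early clustering shrinks the effect to less than one point. This is correct, and it is why a range is given.

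*This belongs in the SAP.* An SAP, not shown, may add missing-data rules, and an exact interval for a crude proportion is a legitimate method. But the protocol already fixes the set and the estimator. An SAP that follows them literally inherits the problem.

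*On 5.4.* Read literally, 11.2 keeps every enrolled volunteer with a dose and a result, so a clarifying sentence may be enough.

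**Conclusion.** The point holds in conditional form. If one negative test is analyzable and testing stops on leaving, the planned primary rate is at or below the FAS members' own full-follow-up rate. It favours the drug if the 35% is a fully observed rate over the same window. Under the stated assumptions at 20% loss, the effect is small to moderate, and the false-success rate rises about one and a half to five times above its no-loss level. The protocol supports neither a claim of outright contradictory denominators nor a certain direction against the 35%. No size is claimed for the mismatch between 5.4 and 11.2. Confidence is medium. This should be changed because a better analysis is available at little cost; it does not invalidate the design.

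**What to change.** - **8.1:** name the FAS as the denominator and say that the four-week phrase describes the regimen.
- **11.3:** estimate cumulative infection in the FAS at one stated week by Kaplan-Meier, censoring at the last negative test, with a complementary log-log 95% interval. Keep the crude Clopper-Pearson percentage as supportive.
- **Tipping point:** Kaplan-Meier assumes non-informative loss, so report how many lost volunteers would have to be infected for the upper limit to reach 35%. For example, with 21 of 104 completers infected and 26 lost without a positive test, 13 more give 34 of 130 (limit 34.6%) and 14 more give 35 of 130 (limit 35.4%), so the answer is 14.
- **5.4 and 11.2:** reconcile them so that, for analysis, these deviations affect PPS membership only and collected test results stay in the FAS. This concerns the analysis and changes no clinical rule.

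Cost: protocol wording and one added analysis, on weekly results that are already planned. The reported rate will be less favourable. At 20% loss with constant hazard and a true 35%, the standard deviation is about 9% larger (4.5 versus 4.1 points) and the mean interval about 5% wider (17.3 versus 16.6 points). At a true 20% rate and 20% loss, Kaplan-Meier meets the assumed success rule in 94.3% to 95.9% of simulated runs, against 97.5% to 99.2% for the crude rate.
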